8.5 Study Drug Accountability

The investigator or designee must maintain an inventory record of study drug administered to assure the regulatory authorities and the sponsor that the investigational new drug will not be dispensed to any person who is not a subject under the terms and conditions set forth in this protocol. Neither the investigators nor any designees may provide study drug to any subject not formally enrolled in this protocol.

The study drug supplied for use in this study is to be prescribed only by the investigator or properly assigned designee and may not be used for any purpose other than that outlined in this protocol.

All unused investigational product will be handled per study drug supplier instructions at conclusion of the study. Periodic review of drug accountability records will be conducted by investigational site monitors. Final review and reconciliation of the accountability records will be performed by the sponsor or designee.

9 Assessments and Procedures

9.1 Schedule of Assessments and Procedures

Table 1 presents the schedule of assessments and procedures to be performed during the study. Assessments are completed per sites' Standard of Care.

Table 1 Schedule of Assessments

Study Assessment ^k	Screening Period	Pretreatment Period	Active Study Period								Follow-up Period (Days from Last Dose)							
			Baseline Assessment	Days 1 to 14 ^a (as applicable)								End of Treatment	7 ± 2 days	14 ± 3 days	30 ± 7 days	90 ± 7 days	180 ± 14 days	365 ± 14 days
				1	2	3	4	5	6	7	8-14							
Diagnosis of HRS - AKI	X																	
Informed consent	X																	
Inclusion exclusion criteria	X	X																
Demographics	X																	
Height, body weight, estimated dry weight ^p	X																	
Pregnancy test ^b	X																	
Prior medications	X	X																
Medical history	X	X																
Physical examination ^d		X																
12-lead ECG ^e	X	X																
Echocardiogram ⁿ		X																
Child-Pugh score		X																
Study drug dosing			X	X	X	X	X	X	X	X	X							

Collaborative Research Study, Version 4: 06/29/21
To Treat HRS-AKI Patients with Continuous Terlipressin Infusion

Study Assessment ^k	Screening Period	Pretreatment Period	Active Study Period								Follow-up Period (Days from Last Dose)										
			Days 1 to 14 ^a (as applicable)								End of Treatment	7 ± 2 days	14 ± 3 days	30 ± 7 days	90 ± 7 days	180 ± 14 days	365 ± 14 days				
		Baseline Assessment	1	2	3	4	5	6	7	8-14											
Biomarker Blood and Urine Sample ^l		X				X					X										
Cystatin c ^m		X			X						X										
Assessments																					
albumin dose if administered	X	X	X	X	X	X	X	X	X	X	X										
SCr ^c (BUN & eGFR if taken ^l)	X	X	X	X	X	X	X	X	X	X	X	X	X	X	X	X	X				
24 hr Urine Volume	X	X	X	X	X	X	X	X	X	X		X									
Vital signs ^h		X	X	X	X	X	X	X	X	X	X										
Encephalopathy score		X	X	X	X	X	X	X	X	X											
Serum electrolytes		X	X	X	X	X	X	X	X	X	X										
ALT, AST, ALP, protein, albumin, bilirubin ^o		X	X	X				X			X	X	X	X	X	X	X				
Serum glucose, calcium, magnesium ^o		X	X	X				X			X										
INR		X	X	X			X			X	X	X	X	X	X	X	X				
CBC ^o		X	X	X			X			X											
Concomitant medications ⁱ			X	X	X	X	X	X	X	X											
Assessments Throughout Study																					
Adverse events ^g			Monitor and record Serious Adverse Events throughout active study period to 30 days post-treatment.																		
Record RRT, TIPS, transplant, and mortality ^j			Monitor and record throughout active study period and follow-up.																		
Record all paracentesis events			Record all paracentesis performed until drug treatment discontinued																		

Collaborative Research Study, Version 4: 06/29/21
To Treat HRS-AKI Patients with Continuous Terlipressin Infusion

All assessments are completed per Standard of Care.

^aMaximum treatment of 14 Days.

^bFemale subjects of child-bearing potential must have a negative urine or serum pregnancy test within 14 days prior to the first dose of study treatment.

^cThe qualifying SCr value (SCr value at least 48 hours after both diuretic withdrawal and the beginning of albumin fluid challenge) is considered the Enrollment SCr and must be drawn prior to start of study drug. The qualifying SCr value must be ≥ 1.5 mg/dL AND Baseline SCr is defined as the most recent, lowest SCr within last 6 months before date of current admission.

^dA general standard of care physical assessment of the major body systems evaluating any new clinically significant abnormalities within the following: general appearance, skin, head/eyes/ears/nose/throat, neck, heart, lungs, abdomen, extremities, and neurological systems. The investigator may perform additional unscheduled examinations to manage or evaluate a suspected AE as clinically necessary. The physical examination will also include weight and height.

^eCollection of the data from the last electrocardiogram done prior to admission and the electrocardiogram performed during admission, if performed as per standard of care

^fMust be performed at least once daily during active treatment AND until Day 14 (regardless of treatment status) or discharge, whichever occurs first. BUN & eGFR are recorded if taken per site standard of care. If assessments are performed more than once daily as part of the subject's medical care, all values are to be recorded on the CRF. If subject has SCr, BUN and/or eGFR, including Vital signs taken at any of the Follow-up Periods, they are to be recorded on the CRF.

^gSerious Adverse Events will be required to be collected only for the Prospective Terlipressin Group.

^hVital sign measurements include body temperature, respiratory rate, systolic and diastolic blood pressure, SpO₂ (pulse oximetric saturation), and heart rate. Vitals will be taken at baseline (within 24 hours of start of study drug) and daily during study drug treatment days. The measurements should be assessed and recorded at a consistent, specific time of day. Preferable morning assessment/measurement.

ⁱConcomitant medications include IV solutions and blood products.

^jAll follow-up visits will include assessments of survival, RRT, TIPS and liver transplant status. Study days will be counted from the last day of study drug administration. If the subject is in the hospital during any of the Follow-up Time Periods, the study assessment data will be recorded from the subject's medical record.

^kAll study assessments are to follow SOC

^lOptional - Collection of Blood and Urine for future biomarker evaluation is optional and may be collected ± 1 day of target collection day

^mOptional - Cystatin C – assessment of cystatin c levels is optional – but if measured we want it assessed 3 times (at Baseline/pretreatment, on day 4 of treatment and last day of treatment)

ⁿCollection of last echocardiogram done prior to admission and any echocardiogram performed during admission, if performed as per standard of care

^oNeutrophils, lymphocytes, total protein, and magnesium if collected Standard of Care

^pEstimated Dry Body Weight is collected if calculated by site

Collaborative Research Study, Version 4: 06/29/21
To Treat HRS-AKI Patients with Continuous Terlipressin Infusion

Table 2 presents the schedule of assessments and procedures to be performed Post Transplantation.

Table 2 **Schedule of Assessments Post Transplantation**

Study Assessment ^c	Day of Liver Transplant	Follow-up Period (Days from Day of Liver Transplant)						
		7 ±2 days ^a	14 ±3 days ^a	30 ±7 days ^a	90 ±7 days ^a	180 ±14 days ^a	365 ±14 days ^a	Last Known follow-up date ^a
Record events of RRT, TIPS and mortality	X	X	X	X	X	X	X	X
Record all paracentesis events	X	X	X	X	X	X	X	X
SCr (BUN & eGFR if taken ^b)	X	X	X	X	X	X	X	X
MELD Score ^d	X							
Dialysis				X	X	X	X	X
Incidence of Kidney Transplant ^e	X	X	X	X	X	X	X	X

^aAll subjects will be contacted for all follow-up periods to assess survival, RRT, TIPS and liver transplant status. Follow-up days will be counted from days after transplantation. If the subject is in the hospital during any of the Follow-up Time Periods, the study assessment data will be recorded from the subject's medical record.

^bBUN & eGFR are recorded if taken per site standard of care. If assessments are performed more than once daily as part of the subject's medical care, all values are to be recorded on the CRF. If subject has SCr, BUN and/or eGFR, including Vital signs taken at any of the Follow-up Periods, they are to be recorded on the CRF.

^cAll study assessments are to follow SOC.

^d In addition to the Allocation MELD score (MELD score that qualifies subject for transplant), also record the date and the last calculated MELD score prior to transplant.

10 Study Assessments

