10.3 Active Study Period (14 Days)

Dosing (Up to 14 Days)

The active study period extends from the initiation of study treatment through Day 14 or discharge from the hospital for any reason, whichever occurs first. Study drug will be administered as described in Section 7.3.2. Concomitant medications will be collected during this active study period. See Table 8.1 for the schedule of assessments during the active study period.

End of Treatment, Discharge or Day 14

Terlipressin may be continued until 24 hours after serum creatinine has reached the lowest value possible as determined by Principal Investigator, up to a maximum of 14 days.

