10.4 Follow-up Period (Up to 365 Days after transplantation)

The follow-up period begins after the end of the study treatment and concludes Day 365 after liver transplantation.

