13.2 Secondary Efficacy Variables

- Improvement of renal function (SCr) from Day 1 through end of treatment, repeated measure analysis as compared to the Retrospective Control Group.
- For the Prospective Terlipressin Group alone and also in comparison to the Retrospective Control Group:
 - Incidence of dialysis by Day 30 and Day 90 of follow up.
 - Survival by Day 30 and Day 90 follow up.
 - Transplant by Day 30 and Day 90 follow up.
 - Serum creatinine at Day 30 and Day 90 follow up
 - Serum creatinine and incidence of dialysis at Day 30, Day 90, Day 180, and Day 365 after liver transplantation
 - Incidence of kidney transplant within one year after liver transplant
 - Descriptive analysis of number simultaneous liver kidney transplants and episodes of graft rejection at Day 90 and Day 365 after liver transplant

14 Serious Adverse Events

Only Serious Adverse Events will be collected for this study for the prospective group only. Safety review and assessments will be made only for the Prospective Terlipressin Group from time of first dose through 30 days after end of treatment. SAEs are collected from the start of study drug until 30 days after study drug was discontinued. Non-serious Adverse Events are not required to be collected for this study.

The investigator will record the nature, causality, severity, treatment, and outcome of the SAE, and will determine whether there is a “reasonable probability” that the study drug treatment caused the event.

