15.2 Secondary Analyses

A number of secondary outcomes will be examined for the study cohort. These outcomes include the incidence of dialysis, mortality, and liver transplantation at day 30 and 90. The

incidence of kidney transplant within one year of liver transplant will also be determined. Additionally, descriptive comparisons of SCr will be undertaken at day 30 and 90 of follow up and at 4 time points after receipt of liver transplantation (day 30, 90, 180 and 365) and also at similar time points for those patients who were transplant ineligible or did not undergo a transplant. Incidence will be calculated as the number of new events during the observation period divided by the total persons at risk. All statistical analyses will be conducted using Stata version 15.1 statistical software (StataCorp, College Park, TX). Statistical significance will be declared for a two-sided hypothesis test if the *P* value was <0.05.

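### Day 30/90 dialysis, survival and transplant are counted from the last dose, which has no defined counterpart in controls, and only controls must have had 48 hours of therapy

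*Combined protocol and SAP*

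**What the plan says.** **Origin.** Table 1 (section 9.1) heads the follow-up columns "Follow-up Period (Days from Last Dose", and footnote j says "Study days will be counted from the last day of study drug administration". Section 10.4 agrees: "The follow-up period begins after the end of the study treatment". Post-transplant time points have their own origin, the transplant date (Table 2).

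**Outcomes.** Section 13.2 lists "Incidence of dialysis by Day 30 and Day 90 of follow up", with survival and transplant at the same days, reported "For the Prospective Terlipressin Group alone and also in comparison to the Retrospective Control Group". Section 15.2 adds: "Incidence will be calculated as the number of new events during the observation period divided by the total persons at risk". It does not say when the observation period starts.

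**Course length.** A terlipressin course lasts up to 14 days. The Synopsis allows one retreatment course, also up to 14 days, within 90 days of first dose. Nothing says whether retreatment moves the last day of study drug for counting purposes.

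**Controls.** The Synopsis applies the same time points to both groups and calls the data collection post-treatment. No section defines the start, end or maximum length of control therapy. The Synopsis, 6.1 and 8.4 require at least 48 hours of it. The Synopsis and 6.1 list midodrine/octreotide, albumin or another vasopressor as alternatives, whereas 8.4 asks for 48 hours of albumin and also of vasopressors.

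**Terlipressin subjects.** The only defined population is the safety population (15.6), which needs one dose. Section 7.5 mentions an Intent-To-Treat analysis but does not define its set.

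**Recording.** For RRT, TIPS, transplant and death, Table 1 says "Monitor and record throughout active study period and follow-up".

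**The concern.** The last dose is a post-baseline date. Under the Synopsis stopping rules it depends on the creatinine course, on RRT and on transplantation, so it is partly set by the outcomes being counted. Measured from treatment start, subjects are followed for windows of different length, and the control window cannot be constructed from the text.

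The 48-hour condition is a second misalignment. A control who dies, is transplanted or otherwise leaves therapy before 48 hours is never selected. A terlipressin subject with the same course stays in. With identical underlying risk, the two groups would still show different Day 30 and Day 90 results.

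**Working it through.** The plan gives no event rate, control course length or power figure for these outcomes, so there is no figure of its own to reproduce. The calendar arithmetic uses the plan's limits. The rest uses stated assumptions.

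**1. Where Day 30 falls.** Call the first dose study day 1.
- The last dose of a single course is on study day 1 to 14, so Day 30 is study day 1 + 30 = 31 to 14 + 30 = 44. Day 90 is study day 91 to 104.
- Retreatment starting 90 days after first dose begins on study day 91, and its 14th day is study day 91 + 13 = 104. If that resets the count, Day 30 is study day 134 and Day 90 is study day 194.

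**2. The 48-hour rule alone.** Inputs: 30-day mortality p = 20%, 30%, 40% or 50% (assumed), the same in both groups, constant hazard, S(t) = (1 − p)^(t/30). Controls are conditioned on surviving 2 days. Counting both groups from treatment start, terlipressin mortality is 1 − S(30) and control mortality is 1 − S(30)/S(2) = 1 − S(28). The difference is S(28) − S(30).
- At p = 0.2: 0.812 − 0.800 = 1.2 points.
- At p = 0.3, 0.4 and 0.5: 1.7, 2.1 and 2.4 points.
- Counting both groups from end of therapy with equal courses of 4 to 14 days gives 1.1 to 2.2 points.

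All of these favour controls.

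**3. Unequal course lengths.** Count both groups from end of therapy, including on-treatment deaths and the 48-hour effect. With lengths LT (terlipressin) and LC (control), the mortality difference is S(28 + LC) − S(30 + LT).

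| Assumed lengths (LT vs LC) | p = 0.2 | 0.3 | 0.4 | 0.5 |
|---|---|---|---|---|
| 7 vs 14 days | −2.8 | −3.7 | −4.3 | −4.6 |
| 14 vs 7 days | +5.0 | +6.7 | +7.8 | +8.4 |

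Negative values favour terlipressin. For example, at p = 0.2 with 7 vs 14 days: S(42) − S(37) = 0.732 − 0.759 = −2.8 points (from unrounded values).

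**4. Precision.** With the 50 and 150 subjects of 15.3 and mortality of 40%: SE = √(0.24/50 + 0.24/150) = √0.0064 = 8.0 points.

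**5. Sensitivity to hazard shape.** With deaths concentrated early, S(t) = (1 − p)^((t/30)^0.6), the 48-hour effect is larger. At p = 0.4, S(2) = 0.904 and control mortality is 1 − 0.600/0.904 = 33.6%, a gap of 6.4 points. At p = 0.2, S(2) = 0.957 and control mortality is 16.4%, a gap of 3.6 points. Exclusion 7 (life expectancy under 7 days) works against such early concentration.

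**6. Cost of a landmark.** Expected deaths within 48 hours among 50 subjects at constant hazard are 50 × (1 − S(2)) = 0.7, 1.2, 1.7 and 2.3 for p = 0.2 to 0.5.

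**The case against.** **Dialysis begun on treatment.** A reader might infer that the plan leaves these starts out, or that its text equally supports very different dialysis rates. The documents do not support that. Exclusion 14 bars RRT in the four weeks before entry, so everyone starts dialysis-free and at risk. An outcome by a given day is naturally cumulative, and Table 1 has RRT recorded in both periods. The natural reading counts on-treatment starts. What stands is a missing sentence in 15.2.

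**Overlapping periods.** Section 10.3 says "The active study period extends from the initiation of study treatment through Day 14 or discharge from the hospital for any reason", whichever comes first. A reader might infer that the active period overlaps follow-up in everyone who stops early. It does not for a subject discharged when dosing ends.

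**A one-dose efficacy set.** The safety population is not an efficacy population, and 7.5 allows some subjects with significant deviations to be left out of the undefined Intent-To-Treat analysis. So one dose is not established as the efficacy entry rule. The text supports less: a 48-hour minimum is stated for controls and none for terlipressin subjects.

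**Weight.** End of treatment is a legitimate origin in itself. These are secondary outcomes in a comparison with historical controls, the Synopsis plans descriptive analysis, and 15.3 already calls the secondary outcomes likely underpowered. Every rate and control course length above is assumed. All of this stands and limits the weight. It does not supply a control origin or make the 48-hour rule symmetric.

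**Conclusion.** The point holds for Day 30/90 dialysis, survival and transplant on the main follow-up schedule. Their origin varies with course length, has no operational equivalent in controls, and is combined with a 48-hour entry condition stated for controls only. The comparison as written is misaligned.

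The likely size is modest. Under assumed 30-day mortality of 20-50% and constant hazard, the 48-hour rule favours controls by about 1-2 points against a standard error of about 8. Early-concentrated deaths would enlarge this, and exclusion 7 would shrink it. Assumed courses of 7 and 14 days move the comparison by about 3-5 points towards terlipressin or 5-8 against it. Dialysis and transplant effects are not quantified here.

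A reader might infer a bias in a known direction. The documents do not support one: control course lengths are not given, and terlipressin subjects may have had midodrine/octreotide before enrolment (note to exclusion 17), which may select the other way. Nor does the point reach the primary creatinine analysis or the post-transplant outcomes, which do not use this origin. It is a cheap improvement of minor-to-moderate weight.

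**What to change.** 1. For Day 30/90 dialysis, survival and transplant, use one index date at the start of the treatment under study: first terlipressin dose, and for controls the first dose of the HRS-AKI regimen given after the qualifying SCr. State that retreatment does not reset it.
2. State in 15.2 that all events from the index date count, including RRT begun on treatment, and that the denominator is all subjects at the index date.
3. For between-group comparisons, apply the same 48-hour landmark to both groups or the minimum to neither, and report how many subjects it removes.
4. Keep Day 30/90 SCr on the existing visit schedule, or use the value nearest the index-based day and report its timing. This needs a rule: after a 14-day course the Day 90 contact falls 13 + 90 = 103 days after first dose, outside a 90 ± 7 day window.
5. Abstract the control therapy start date, and the RRT start date in both groups.
6. Separately, reconcile 8.4 with the Synopsis and 6.1 on whether controls need albumin, a vasopressor or both.

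The cost is wording in the Synopsis, 6.1, 8.4, footnote j, 10.4 and 15.2, plus two abstracted dates. No new visits are needed. A landmark would drop about 1-2 of 50 terlipressin subjects through early deaths under the assumed rates, plus any who stop or are transplanted before 48 hours, and it conditions on remaining in treatment. Prior midodrine/octreotide leaves some misalignment, which should be reported.

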10.1 Screening Period

The screening period occurs prior to enrollment and consists of establishing the diagnosis of HRS-AKI as per guidelines and standard medical practice and confirming eligibility for study participation. The investigator or qualified designee will not be required to obtain sponsor approval to enroll subjects. Enrollment of subjects determined not to qualify for the study during sponsor monitoring oversight may result in study site closure. Written informed consent will be obtained by the investigator, sub-investigator, or qualified designee from the subject or legally authorized representative prior to the subject qualification form being completed.

10.2 Pre-Treatment Period

The pre-treatment period occurs prior to administration of study drug and includes performing baseline assessments and collection of prior medication information.

The qualifying SCr value (SCr value at least 48 hours after both diuretic withdrawal and after the beginning of albumin fluid challenge) is considered the enrollment SCr and must be drawn prior to study drug administration.

10.3 Active Study Period (14 Days)

Dosing (Up to 14 Days)

The active study period extends from the initiation of study treatment through Day 14 or discharge from the hospital for any reason, whichever occurs first. Study drug will be administered as described in Section 7.3.2. Concomitant medications will be collected during this active study period. See Table 8.1 for the schedule of assessments during the active study period.

End of Treatment, Discharge or Day 14

Terlipressin may be continued until 24 hours after serum creatinine has reached the lowest value possible as determined by Principal Investigator, up to a maximum of 14 days.

10.4 Follow-up Period (Up to 365 Days after transplantation)

The follow-up period begins after the end of the study treatment and concludes Day 365 after liver transplantation.

10.5 Physical Examination

A physical examination, including weight, estimated dry weight (if calculated as per standard of care), and height, will be conducted at baseline and will follow the standard of care for these subjects.

The investigator may perform additional unscheduled examinations to manage or evaluate a suspected SAE as clinically necessary. The timing and scope of additional unscheduled examinations should be determined by the nature and severity of the SAE being evaluated.

